e) Describe alternative procedures or courses of treatment, if any, that might be advantageous to the participant. Describe potential risks and benefits associated with these. Any standard treatment that is being withheld must be disclosed in the consent process and form. (i.e. standard-of-care drug, different interventional procedure, no procedure or treatment, palliative care, other research studies).

The alternative is not to participate in the study. As there is no formal intervention component to the current study, there is no alternative treatment course for those who do, versus those who do not, participate in the study. All participants will have access to substance use treatment within VA, consistent with treatment guidelines.

f) Will it be possible to continue the more (most) appropriate therapy for the participant(s) after the conclusion of the study?

The outpatient SUD treatment program is currently available at the VA Palo Alto. Thus, patients can utilize it at any time. The VAPAHCS also offers cognitive behavioral therapy for insomnia which can be accessed by veterans.

g) Study Endpoint. What are the guidelines or end points by which you can evaluate the different treatments (i.e. study drug, device, procedure) during the study? If one proves to be clearly more effective than another (or others) during the course of a study, will the study be terminated before the projected total participant population has been enrolled? When will the study end if no important differences are detected?

Title: The Impact of CBT-I on Cannabis Cessation Outcomes
Approval Period: 03/27/2015 - 03/11/2016

N/A.

3. Background

a) Describe past experimental and/or clinical findings leading to the formulation of the study.

The Prevalence of cannabis use disorder (CUD) has been steadily increasing within the Veteran Health Administration (VHA), along with the related significant physical, cognitive, and psychological sequelae. Even in patients with a strong motivation to quit and the presence of empirically-supported interventions (Roffman & Stephens, 2006), Veterans who receive treatment for CUD have high rates of lapse (63% by 6-months post-treatment) and relapse (71% within 6-months post-treatment; Moore et al., 2003). Thus, identifying strategies to improve response to CUD treatment is in the interest of all VHA stakeholders.

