Participant retention strategies are based on strategies successfully used in past research designs by members of this research team. Based on previous prospective designs, the risk for participant attrition may occur at 3 main time points: baseline, during treatment, and follow-up. We will specifically address each time point to limit attrition rates. First, it is expected that a small number of individuals will not complete the baseline assessment. In this case, those individuals will be excluded from data analysis and replaced with another participant. In relation to prospective retention, of those completing baseline procedures, we expect 80% of the original sample to complete all follow-up assessments (Heinz et al., 2013; also see section 2a.3, “Missing Data” subsection). *We will recruit 187 Veterans in order to account for 10% attrition from baseline to the group intervention, with the goal of randomizing 168 Veterans.* In addition, an intent-to-treat approach will be used for all analyses. *Within the intent-to-treat approach individuals completing at least 70% of the intervention/control group will be included in all analyses, thereby limiting the impact of the predicted 20% attrition.* Finally, we will employ a multi-pronged approach to enhance participation in all follow-up assessments. This approach will utilize financial incentives, participant contact, and session reminders.

Financial Incentives. To reduce attrition rates, a weighted compensation schedule will be employed as follows: Baseline assessment (\$50), post-treatment/placebo group (6-weeks) (\$50), 2-weeks post-cessation (\$25), 4-weeks post-cessation (\$25), and 6-months post-cessation (\$25), with a \$60 bonus for individuals that completed all time points. Overall, the rate of compensation was determined based on \$19/hour of daytime assessment.

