In terms of the primary hypothesis of Aim 1 (Hypothesis 1.1), *the impact of CBT-I-MA and CBT-I on frequency of cannabis use post-cessation, we based our power calculations on an ANCOVA with the inclusion of 3 covariates as this would provide an overestimation of the sample size required for the GLMM analysis. A sample of 168 individuals would allow for a detection of a significantly smaller effect in terms of the primary aim ($d = .42$), providing confidence in our ability to detect the hypothesized effect of $d = 1.4$. This sample size will also allow for adequate power to detect group differences between CBT-I-MA and CBT-I ($d = .42$; Aim 1 Exploratory Hypothesis)*.

In terms of the secondary hypothesis of Aim 1 (Hypothesis 1.2), *the impact of CBT-I-MA and CBT-I on PPA, we used power calculation software to calculate the effect size based on a test of independent proportions. With an estimated abstinence rate of 20% within the placebo condition (PC; based on previous research; Marijuana treatment project research group, 2004), and alpha of .05, 168 Veterans (56 per group) will allow for power of .80 to detect a 30% difference in the prevalence of abstinence in the CBT-I group. As we conservatively estimate a 50% abstinence rate in the CBT-I condition, we will have enough power to detect the expected effect*.

In terms of Aim 2, investigating the role of CBT-I-MA and CBT-I on subjective and objective sleep quality, *we based our power analysis on an ANCOVA with the inclusion of 3 covariates and 3 groups as this would overestimate the required sample size needed within GLMM models. A sample of 168 individuals would allow for a detection of a smaller effect in terms of the primary aim ($d = .42$), providing confidence in our ability to detect the hypothesized conservative effect of $d = .56$. This will also allow for adequate power to detect group differences between CBT-I-MA and CBT-I ($d = .42$; Aim 2 Exploratory Hypothesis)*.

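### The power stated for Hypothesis 1.2 does not match its stated inputs: 56 per group gives about .93 (.89 with continuity correction) for 20% v 50% abstinence, and .80 fits about 45 per group

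*SAP*

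**What the plan says.** The relevant paragraph is the one on Hypothesis 1.2 in the SAP's Power Analysis.

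- **Method:** "we used power calculation software to calculate the effect size based on a test of independent proportions". It does not say which test, whether it is one- or two-sided, or whether a continuity correction was applied.
- **Inputs and result:** with 20% abstinence on placebo and alpha .05, "168 Veterans (56 per group) will allow for power of .80 to detect a 30% difference in the prevalence of abstinence". The active rate follows: "As we conservatively estimate a 50% abstinence rate in the CBT-I condition".
- **Attrition:** this paragraph makes no allowance for it. Section 2a.3.f (Participant Retention) says "we expect 80% of the original sample to complete all follow-up assessments".
- **Analysis set:** the last paragraph of the Power Analysis says that everyone randomized is analysed.
- **Source of 168:** the same section derives the total sample from the mediation test, as the most demanding analysis, and then checks the other hypotheses against it.

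**The concern.** The paragraph gives everything a two-proportion power calculation needs except the sidedness and the correction, so a reader can check it. The check does not return the stated power. Either the number per group or the power belongs to a different calculation from the one described.

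What is at stake is interpretation, not the viability of the trial. Someone reading a null abstinence result needs to know what difference the trial could have detected, and on how many analysed participants. As written, a power that appears to belong to a depleted sample is attached to the full randomized sample.

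**Working it through.** **Inputs.** From the SAP's Hypothesis 1.2 power paragraph: p1 = .20, p2 = .50, alpha = .05, n = 56 per group. From section 2a.3.f: 80% complete all follow-up, so 56 × .80 = 44.8, or about 45 per group. My assumption: a two-sided test, z = 1.96.

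**Formula.** Pooled variance under the null, unpooled under the alternative, with p̄ = (.20 + .50)/2 = .35:

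- SE0 = √(2 p̄(1 − p̄)/n)
- SE1 = √([p1(1 − p1) + p2(1 − p2)]/n)
- power = Φ((|p2 − p1| − c − 1.96 × SE0)/SE1), where c = 0 uncorrected and c = 1/n with continuity correction

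**Stated inputs, n = 56.**

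- SE0 = √(2 × .35 × .65/56) = .0901
- SE1 = √((.16 + .25)/56) = .0856
- Uncorrected: (.30 − .1767)/.0856 = 1.44, power .925
- Corrected (1/56 = .0179): (.2821 − .1767)/.0856 = 1.23, power .891

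**Other tests at 56 v 56, alpha .05.** Arcsine gives .926, Fisher's exact .898 and one-sided .962. The full span is .89 to .96, so none gives .80.

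**Looking for .80.** Without correction, .80 needs only 39 per group. With correction it needs 45:

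- SE0 = √(2 × .35 × .65/45) = .1006
- SE1 = √(.41/45) = .0955
- Uncorrected: (.30 − .1971)/.0955 = 1.08, power .860
- Corrected (1/45 = .0222): (.2778 − .1971)/.0955 = .845, power .801

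So .80 can be reproduced with two things the paragraph leaves out: a continuity correction and the SAP's own 20% loss. Working back, 45/.80 = 56.25, close to the stated 56. Other unstated routes also come near .80. Fisher's exact test at 44 per group gives .802, and 56 per group at alpha .01, uncorrected, gives .786. The route actually taken therefore cannot be settled from the text.

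**Smallest abstinence rate detectable at power .80 against 20%.**

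| Analysed per group | Power, 20% v 50%: uncorrected | corrected | Detectable rate: uncorrected | corrected |
|---|---|---|---|---|
| 56 | .93 | .89 | 44.5% | 46.5% |
| 45 | .86 | .80 | 47.6% | 50.0% |

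**The case against.** The best defence is that nothing is miscalculated. The SAP is silent on correction and attrition, and supplying plausible values for both recovers .80 almost exactly, using the SAP's own completion rate. On that view the fault is incomplete reporting. The figure is also cautious, and 168 does not depend on it. Much of this stands. The sponsor's calculation may well have been sound, and the sample size is safe. What does not stand is the sentence as printed: it ties .80 to 56 per group, while the same section says all randomized participants are analysed. A reader cannot get from those inputs to that output.

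Two technical reservations also stand. The planned analysis of Hypothesis 1.2 is a mixed-effects logistic regression over three visits, so any two-proportion power, including the SAP's, is an approximation. And 45 per group counts only those who complete every follow-up; partial completers would also contribute to that model.

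A reader might infer something stronger from Protocol section 3a, which reports "high rates of lapse (63% by 6-months post-treatment) and relapse (71% within 6-months post-treatment" among treated Veterans. The complements are 37% and 29%. Holding CBT-I at 50%, power at 56 per group (uncorrected) would be .28 against 37% and .63 against 29%. The documents do not support presenting this as a contradiction or as the trial's real power:

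- Section 3a gives no denominators or definitions, and it puts relapse above lapse. That ordering cannot hold on one denominator if everyone who relapses has first lapsed.
- Never having lapsed would be a floor for point prevalence abstinence only on a common denominator. Not having relapsed is no floor at all, since such a person may have lapsed and be using at the visit.
- Every trial participant has insomnia, and section 3a itself says disturbed sleep raises lapse and relapse. The current protocol also no longer requires motivation to quit. A placebo rate below 37% is compatible with both.
- The low power comes from shrinking the effect to 13 or 21 points. With the SAP's 30-point difference kept, power at 56 per group is .899 (37% v 67%) and .903 (29% v 59%).

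**Conclusion.** The stated power and the stated number per group do not belong together. On the paragraph's own inputs power is about .93, or .89 with continuity correction, so .80 understates it by roughly .09 to .13. The .80 fits about 45 per group with a continuity correction; that this was the sponsor's route is an inference. The conclusion rests on a two-sided test at alpha .05, but no standard test at 56 v 56 and that alpha gives .80, and a one-sided test moves further away.

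The mismatch is in the safe direction: 56 per group is more than enough for 20% v 50%, and even 45 per group reaches .80. The lapse and relapse rates in Protocol section 3a do not contradict the 20% placebo assumption. At most they are a reason to show how power varies with the placebo rate.

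**What to change.** Restate the Hypothesis 1.2 power paragraph in the SAP:

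1. Name the test, its sidedness and whether a continuity correction is used.
2. Give power for 20% v 50% as .93 (.89 corrected) with 56 per group analysed and .86 (.80 corrected) with 45 per group, and say that 45 reflects the 20% follow-up loss in section 2a.3.f.
3. Give the smallest abstinence rate detectable at power .80 against 20%: about 44-47% with 56 per group and 48-50% with 45. The lower figure is uncorrected and the upper corrected.
4. Optionally, add a short sensitivity table over other placebo rates, stating in each row whether the 50% active rate or the 30-point difference is held fixed, since that choice drives the answer.

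The cost is SAP wording only. Sample size, conduct and planned analyses do not change.
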